8.2 Screening

All participants must provide a signed main ICF prior to performing any study specific procedures and will be evaluated for eligibility.

The screening assessments will be done within 28 days prior to the enrollment (Section 8). Laboratory parameters may be retested within the 28-day screening period for an individual participant if such parameters meet an exclusion criterion when initially tested.

Laboratory values obtained during the Screening period from the central laboratory will be used to assess participant's eligibility, except for China, where local laboratory results can be used for eligibility. If necessary, for immediate clinical decision locally unscheduled testing may be performed and used for eligibility.

Laboratory assessments performed as part of the screening evaluations will not be required to be repeated on the first day of dosing (except for hematology/chemistry and serum pregnancy test if not done within 72 hours prior to treatment start) unless considered clinically necessary by Investigator and/or required as per local institutional policies.

Imaging assessments will be performed at screening between Day -28 and Day -1. Imaging assessments already completed during the regular work-up of the participant within 28 days prior to start of treatment (-42 days for whole body scan), including before signing the main study ICF can be considered as the baseline images for this study. Any imaging assessments obtained after enrollment cannot be considered baseline images.

Participants who are enrolled in the IRT system and failed to start treatment, e.g. participants confirmed in IRT in error, will be considered as early terminators. The reason for early termination should be recorded on the appropriate eCRF.

8.2.1 Eligibility screening

When all screening procedures are completed and once the participant's eligibility has been checked and confirmed (i.e., all inclusion/exclusion criteria have been verified), the key eligibility criteria checklist will be completed prior to the first dose of study treatment in the IRT system by the Investigator or designee. The eligibility check will be embedded in the IRT system.

Please refer Section 6.3.1 and comply with detailed guidelines in the IRT manual.

8.3 Participant demographics/other baseline characteristics

Country-specific regulations should be considered for the collection of demographic and baseline characteristics in alignment with eCRF.

Data to be collected on participant characteristics at pre-screening include:

• Demography: age, sex, race/predominant ethnicity (if permitted). Participant race/ethnicity data should be collected wherever allowable by local laws and regulations. These data are collected and analyzed to identify any differences in the safety and/or efficacy profile of

the treatment due to these characteristics. In addition, these data are necessary to assess the diversity of the study population as required by Health Authorities.

- Cancer characteristics including diagnosis, history, extent of disease
- Information on tumor samples submitted to the central laboratory for testing
- PD-L1 status per participant's record (where available)
- KRAS G12C and STK11 mutation status per participant's record (where available)

Data to be collected on participant characteristics at screening include:

- Molecular alteration status of EGFR, ALK and other genes which are druggable, per participant's record
- Other background or relevant medical history/current medical conditions (until date of signature of informed consent) including smoking / vaping history
- Prior antineoplastic therapies (medications, radiation, surgeries), and date of progression/recurrence prior to study entry
- Tumor imaging assessment
- Other assessments to be completed for the purpose of determining eligibility (ECOG, PS, complete physical examination, vital signs, hematology, blood chemistry, coagulation, urinalysis, serum pregnancy test for women of child-bearing potential [only recorded in source documentation], 12-Lead ECG and Cardiac Imaging)
- Prior and current concomitant medications and surgical and medical procedures (All
 prescription medications, over-the-counter drugs and significant non-drug therapies prior
 to the start of the study must be documented. See the protocol Section 6.8 Concomitant
 Therapy for further details on what information must be recorded on the appropriate page
 of the eCRF).

Data to be collected on participant characteristics at C1D1 (pre-dose) include:

PRO assessments

8.4 Efficacy assessments

Planned time points for all efficacy assessments are provided in Section 1.3 Schedule of Activities.

8.4.1 Tumor assessment

Tumor response will be assessed both locally and centrally according to the Novartis guideline version 3.2 (Appendix 8 Section 10.8) based on RECIST 1.1 (Eisenhauer et al 2009).

The central review of the scans will be carried out in a blinded fashion. Imaging data will be centrally collected and checked for quality by an imaging Contract Research Organization (CRO) designated by Novartis (Details of the central review process will be described in the independent review charter).

Information regarding biopsy results, prior interventions (e.g., radiotherapy), pre-existing radiographic findings that mimic metastatic disease at baseline/screening and prior interventions should be transmitted to the imaging CRO with the baseline images for review by

the independent radiologist. Sites must transfer information as specified in the imaging CRO site manual and ensure the data is consistent with the data entered in the clinical database.

The CT scan component of the FDG-PET/CT should be used for treatment response assessment only if the CT is of similar diagnostic quality as a CT performed without PET, including the utilization of i.v. contrast media. At the discretion of the Investigators, FDG-PET scans may be performed to document progressive disease per RECIST 1.1 (Section 10.8).

The imaging assessment collection plan is presented in Table 8-1.

Table 8-1 Imaging Assessment Collection Plan

Procedure	Screening/Baseline (within 28 days prior to start of treatment)	During Treatment/Follow-up
Chest, abdomen and pelvis CT or MRI (with intravenous contrast enhancement)#	Mandated	During Treatment: Mandated, every 6 weeks (+/- 7 days) from C1D1 until Week 54, then every 12 weeks (+/- 7 days) until confirmed PD* During Post Treatment Follow-Up: participants with EOT reason other than disease progression, withdrawal of consent/opposition to use data/biological samples or death will continue to collect imaging and follow the same schedule of every 6 weeks (+/- 7 days) for the 54 weeks after C1D1, then every 12 weeks (+/- 7 days), thereafter until confirmed PD*
Brain MRI or CT	Mandated	If brain metastases are present at baseline During Treatment: Every 6 weeks (+/- 7 days) from C1D1 up to 54 weeks and every 12 weeks (+/- 7 days) thereafter until confirmed PD*. During Post Treatment Follow-Up: Participants with EOT reason other than disease progression, withdrawal of consent/opposition to use data/biological samples or death will continue to collect imaging and follow the same schedule proposed during treatment. If no brain metastases are present at baseline During Treatment: Every 12 weeks (+/- 7 days) from C1D1 until confirmed PD*. During Post Treatment Follow-Up: Participants with EOT reason other than disease progression, withdrawal of consent/opposition to use data/biological samples or death will continue to collect imaging and follow the same schedule proposed during treatment. Otherwise, if clinically indicated
Whole body bone scan (Per institutional standard of care [e.g., Tc-99m bone scan, whole body bone MRI, 18F - fluorodeoxyglucose positron emission tomography (FDG-	Mandated (within 42 days prior to start of treatment)	If clinically indicated.

Procedure	Screening/Baseline (within 28 days prior to start of treatment)	During Treatment/Follow-up
PET) or 18 F - sodium fluoride (NaF) PET])		
Localized bone CT, MRI, or x-ray	Mandated for any lesions identified on the whole-body bone scan that are not visible on the chest, abdomen, and pelvis CT or MRI.	If lesions were documented at baseline, follow same schedule as CT/MRI of chest, abdomen, and pelvis. Otherwise, if clinically indicated
Color photography (with scale/ruler)	If clinically indicated,in case skin metastatic lesions are present.	If lesions were documented at baseline, follow same schedule as CT/MRI of chest, abdomen, and pelvis. Otherwise, if clinically indicated
CT or MRI of other metastatic sites (e.g., neck)	If clinically indicated	If lesions were documented at baseline, follow same schedule as CT/MRI of chest, abdomen, and pelvis. Otherwise, if clinically indicated

^{*}Progression by RECIST 1.1 as confirmed by BIRC.

Baseline imaging assessments

Any imaging assessments already completed during the regular work-up of the participant within 28 days prior to start of treatment (42 days for whole body bone scan), including before signing the main study ICF, can be considered as the baseline images for this study. Any imaging assessments obtained after C1D1/enrollment cannot be considered baseline images. The following assessments are required at screening/baseline:

- Chest, abdomen, and pelvis CT or MRI (Combined Positron Emission Tomography (PET)/CT may be used if the CT component is of similar diagnostic quality as a CT performed without PET, including the utilization of i.v. contrast media)
- Brain MRI or CT
- Whole body bone scan
- Localized bone CT, MRI, or x-ray, for any lesions identified on the whole-body bone scan that are not visible on the chest, abdomen and pelvis CT or MRI
- Color photography for any skin metastatic lesions present, if clinically indicated
- CT or MRI of other metastatic sites (e.g., neck), if clinically indicated

If a participant is known to have a contraindication to CT intravenous (IV) contrast media or develops a contraindication during the trial, a non-contrast CT of the chest (MRI is not recommended due to respiratory artifacts; however, if CT is not feasible per local regulations, MRI can be performed instead) plus a contrast-enhanced MRI (if possible) of the abdomen and pelvis should be performed.

Brain MRI or CT should be completed. Contrast enhanced brain MRI is preferred. However, if MRI contrast is contraindicated, then MRI without contrast or CT with contrast are acceptable.

A whole-body bone scan should be performed per institutional standard of care [e.g., Tc-99m bone scan, whole body bone MRI, 18F- fluorodeoxyglucose positron emission tomography

[#] Combined Positron Emission Tomography (PET)/CT may be used for treatment response assessment if the CT component is of similar diagnostic quality as a CT performed without PET, including the utilization of i.v. contrast media.

(FDG-PET) or 18 F-sodium fluoride (NaF) PET]. Localized CT, MRI, or X-rays should be acquired for all skeletal lesions identified on the screening whole body bone scan which are not visible on the chest, abdomen and pelvis CT/MRI.

If clinically indicated, CT or MRI of other areas (e.g., neck) of disease should be performed.

If skin metastatic lesions are present at screening, color photography should be acquired (if clinically indicated) using a digital camera in clear focus, including a scale/ruler, in such a way that the size of the lesion(s) can be determined from the photograph.

Any potentially measurable lesion that has been previously treated with radiotherapy should be considered as a non-measurable lesion. However, if a lesion previously treated with radiotherapy has clearly progressed since the radiotherapy, it can be considered as a measurable lesion.

Chest x-rays and ultrasound should not be used to measure tumor lesions.

Post-baseline imaging assessment

Imaging assessments as described in Table 1-3 and Table 8-1 should be performed using the same imaging modality used at baseline, irrespective of study treatment interruption or actual dosing.

Imaging assessments should be scheduled using the date of first dose (C1D1) as the reference date (not the date of the previous tumor assessment), and this schedule should be respected regardless of whether treatment with study treatment is temporarily withheld or unscheduled assessments performed.

Additional imaging assessments may be performed at any time during the study at the Investigator's discretion to support the efficacy evaluations for a participant, as necessary. Clinical suspicion of disease progression at any time requires a physical examination and imaging assessments to be performed promptly rather than waiting for the next scheduled imaging assessment.

If an off-schedule imaging assessment is performed because progression is suspected, subsequent imaging assessments should be performed in accordance with the original imaging schedule.

Time points at which progression is determined locally

For participants who have disease progression determined by the local Investigator, an expedited central review is required. Rapid image transmission to the imaging CRO should be accomplished by transferring the images electronically. In all instances, the process at the imaging CRO will ensure that the central reviewers remain blinded to the results of the local assessment and the expedited nature of the review. The Investigator seeking an expedited review must indicate this request to the imaging CRO at the time of image submission. The imaging will undergo expedited central review (within 5 business days from the time of image receipt at the imaging CRO and once all applicable queries are resolved) and the results of the central review will be communicated to the site. While the Investigator is awaiting the results

of the central review, it is preferable that the participant continues on study treatment. However, during this time, the Investigator should do whatever is medically necessary for the participant.

If the central review confirms disease progression, then the participant will discontinue study treatment and subsequent tumor assessments are no longer required unless the criteria are met to continue study treatment beyond disease progression per RECIST 1.1 (for participants treated with JDQ443 only) as described in Section 6.1.4.1.

If the central review does not confirm disease progression, the participant should continue receiving the study treatment until disease progression has been confirmed by BIRC at a subsequent visit or, as a minimum requirement, until at least one additional tumor assessment has been completed, unless there is a medical need (i.e., rapid progression or clinical deterioration) for an immediate change in therapy.

In summary, for expedited timepoints (assessed as progressive disease by local):

Rapid image transmission to the central imaging CRO may be accomplished by uploading all digital images acquired by the Investigator in a secured website, while preserving the blinded status of the images.

- If central radiology confirms progressive disease, the study site will be informed. This participant should then discontinue study treatment. Participants treated with JDQ443 may continue study treatment beyond disease progression per RECIST 1.1 if according to investigator's judgement the participant is benefiting from study treatment and if certain conditions are met, as described in Section 6.1.4.1.
- If central radiology does not confirm progressive disease, the study site will be informed. As long as it is clinically acceptable, every effort should be made to continue the participant on study treatment until progressive disease is confirmed by BIRC or for at least one subsequent radiological timepoint.

Time points without locally determined progression

All imaging time points without locally determined progression will be read on an ongoing, non-expedited basis as detailed in the imaging manual to be provided by the designated imaging CRO and independent review charter. Results of these readings will not be communicated to the sites.

Treatment beyond disease progression

Following determination of disease progression, if the Investigator believes the participant treated with JDQ443 may derive benefit from continuing study treatment, the participant will be permitted to continue treatment beyond initial disease progression as per RECIST 1.1 by BIRC. Please see Section 6.1.4.1 for additional information.

Efficacy follow-up imaging assessments

For participants who discontinue treatment for reasons other than initial disease progression as per RECIST 1.1, tumor assessments must continue to be performed as outlined in Table 1-3 regardless if participants start on new antineoplastic therapy before documented disease progression. Please refer to Section 8.4 for additional information.

As per Section 4.5, during a Public Health emergency as declared by Local or Regional authorities i.e., pandemic, epidemic or natural disaster, that limits or prevents on-site study visits, the collection of images (e.g., change of imaging center or imaging frequency) may be modified by Novartis and will be communicated to the Investigator.

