NSCLC-SAQ ⁷			Day 1 of 0 Then on Da	ay 1 only s				Х		Every 12 weeks and at disease progression per RECIST 1.17	Post disease progression, every 12 weeks for a minimum of 3 timepoints
EORTC QLQ-C30 ⁷			Day 1 of Cy		cle 2, Cyc les therea		en every 3	Х		Every 12 weeks and at disease progression per RECIST 1.17	Post disease progression, every 12 weeks for a minimum of 3 timepoints

Period			Trea	atment		Fo	llow-up				
Cycle					Cy	/cle 1				-	
Visit Name	Molecular Pre- screening	Screening	Cycle	e 1	Cycle 2		Cycle 3 onwards	ЕОТ	Safety follow-up (30 days after last administration of stud treatment)	Efficacy follow-up	Survival follow- up (every 12 weeks)
Days	0	-28 to -1	Day 1	Day 15	Day 1	Day 15	Day 1	-	-	-	-
FACT GP5 ⁷			Day 8 of 0 Then on Da	y 1 only s		7 days unt Cycle 4 fo		х		Every 12 weeks and at disease progression per RECIST 1.17	Post disease progression, every 12 weeks for a minimum of 3 timepoints
PRO CTCAE ⁷			Day 1 of 0 Then on Da	y 1 only s				х		Every 12 weeks and at disease progression per RECIST 1.16	Post disease progression, every 12 weeks for a minimum of 3 timepoints
Patient Global Impression of Severity of Symptoms- NSCLC symptoms) (PGIS-NSCLC) ⁷			Day 1 of 0 Then on Da	y 1 only s				х		Every 12 weeks and at disease progression per RECIST 1.17	Post disease progression, every 12 weeks for a minimum of 3 timepoints
EQ5D-5L ⁷			Day 1 of Cy		cle 2, Cyc les therea		en-every 3	х		Every 12 weeks and at disease progression per RECIST 1.17	Post disease progression, every 12 weeks for a minimum of 3 timepoints
Blood plasma for exploratory analysis of			х	х			C3 day 1	Х			

Period	Scree	ening			Tre	atment		Fo	ollow-up				
Cycle					C)	/cle 1							
Visit Name	Molecular Pre- screening	Screening	Cycle	e 1	Cycle 2		Cycle 3 onwards	ЕОТ	Safety follow-up (30 days after last administration of study treatment)	Efficacy follow-up	Survival follow- up (every 12 weeks)		
Days	0	-28 to -1	Day 1	Day 15	Day 1	Day 1 Day 15		-	-	-	-		
(collected before treatment administration)													
CT or MRI of chest, abdomen and pelvis		х	Every 6	Every 6 weeks counting from C1D1 up to 54 weeks and every 12 weeks thereafter until disease progression (by RECIST 1.1) is confirmed by BIRC									

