7.1.2 Follow-up for efficacy evaluations and PROs

Participants who discontinue study treatment without prior documented disease progression will continue efficacy assessments during the post-treatment efficacy follow-up, until documented disease progression per RECIST 1.1 by BIRC, participant withdrawal of consent/opposition to use of data /biological samples, investigator's decision, lost to follow-up, death or if study is terminated by the sponsor. For all participants, PRO will also continue to be collected (PRO Follow-up) until documented progression, and at a minimum of three time points following disease progression (refer to Section 8.6.1). All SAEs reported during this time period must be reported as described in Section 8.7.

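### Protocol Table 8-1 selects participants for post-treatment scans by an EOT reason of disease progression without naming BIRC, in conflict with the BIRC-based rules elsewhere; a minor risk to BIRC DOR and PFS.

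*Protocol*

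**What the plan says.** Table 8-1 (Protocol 8.4.1) sets the post-treatment imaging rule for chest, abdomen and pelvis: "participants with EOT reason other than disease progression, withdrawal of consent/opposition to use data/biological samples or death will continue to collect imaging". The two brain entries, with and without brain metastases at baseline, repeat the same exclusions and end: "death will continue to collect imaging and follow the same schedule proposed during treatment". In all three entries the assessor of progression is left open. The table's footnote does name one, "Progression by RECIST 1.1 as confirmed by BIRC", but it is attached to the confirmed PD at which scans stop, not to the EOT reason that decides who is scanned.

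Two other texts say who continues:

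- The efficacy follow-up paragraph of 8.4.1 covers "participants who discontinue treatment for reasons other than initial disease progression as per RECIST 1.1, tumor assessments must continue to be performed". It names RECIST 1.1 but not BIRC, and the sentence goes on to refer to Table 1-3.
- Section 7.1.2 opens: "Participants who discontinue study treatment without prior documented disease progression will continue efficacy assessments". It names no assessor there, but it ends the follow-up with "until documented disease progression per RECIST 1.1 by BIRC".

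Table 1-3 (Protocol 1.3) sets no condition on the reason for ending treatment. Body imaging runs every 6 weeks to week 54, then "every 12 weeks thereafter until disease progression (by RECIST 1.1) is confirmed by BIRC".

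**The concern.** Treatment in this trial can end for progression that BIRC has not confirmed. A site that then consults Table 8-1, the imaging collection plan, finds a participant whose EOT reason is disease progression and can conclude that no further scans are due. Table 1-3 says the opposite.

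DOR by BIRC is a key secondary endpoint and PFS by BIRC is secondary, and both need those scans. Without them, a later BIRC progression is not seen and the participant is censored at the last adequate assessment. The people censored this way are those just judged to be worsening. The censoring is therefore informative and tends to lengthen BIRC DOR and PFS.

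**Working it through.** The plan gives no figure to reproduce, so the check is a comparison of texts, followed by the SAP censoring rules and an illustration of size.

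**1. Where BIRC is named**

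| Text | Role | Assessor |
|---|---|---|
| Table 8-1, body row and both brain entries | who is scanned | none |
| 8.4.1, efficacy follow-up paragraph | who is scanned | RECIST 1.1, no BIRC; refers to Table 1-3 |
| 7.1.2, opening clause | who is scanned | documented progression, no BIRC |
| 7.1.2, closing clause | when scans stop | BIRC |
| Table 8-1 footnote | when scans stop | BIRC |
| Table 1-3 | when scans stop | BIRC |
| 8.4.1, locally determined progression | when scans are no longer required | central review |
| 8.6.1, PRO schedule | who enters efficacy follow-up | BIRC |

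Table 8-1 is the only text loose enough to cover clinical progression. The other two loose texts leave open, at most, RECIST or documented progression that BIRC did not confirm.

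**2. Can treatment end for progression without BIRC PD?** Yes. After a local PD that BIRC does not confirm, 8.4.1 asks for treatment until BIRC PD or at least one more assessment, "unless there is a medical need (i.e., rapid progression or clinical deterioration) for an immediate change in therapy". Appendix 8 (10.8.4.2) lists progressive disease as a discontinuation reason with no assessor, and 10.8.4.4 accepts that reason for documented symptomatic deterioration. SAP Table 2-6 has a row for the case.

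**3. What the analysis then does**

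- Clinical progression is not an event (Protocol Table 10-12, situation E, default option; SAP 2.8.1.4). Appendix 8 justifies this by expecting such participants to be followed for progression after treatment.
- The DOR estimand uses a treatment-policy strategy for discontinuation (SAP 1.2.2, 2.7.3), which presumes post-treatment scans.
- With no event, DOR and PFS are censored at the last adequate assessment (SAP 2.7.4, 2.8.1.4).
- A death counts only within D2 of that assessment (SAP 4.5). D2 is 2 × 6 + 2 = 14 weeks, 6 + 12 + 2 = 20 weeks or 2 × 12 + 2 = 26 weeks, depending on when the last adequate assessment fell.

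**4. Who is exposed.** New anticancer therapy censors DOR and PFS anyway (SAP Table 2-6). The avoidable loss is confined to participants who start no new therapy, and to the interval before new therapy in those who do.

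**5. Illustration of size, participants with no next line.** Inputs:

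- share stopping for progression without BIRC PD, s = 5% to 20% (assumed; the documents give no rate);
- share receiving no next line, r = 40% to 50% (Protocol 2.2.4, a general figure for advanced NSCLC);
- ORR 45% (assumed);
- exponential survival after the last scan, median 3 to 9 months (assumed);
- every site takes the literal reading (assumed).

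Exposed share = s × r: 0.05 × 0.40 = 0.02 to 0.20 × 0.50 = 0.10.

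- Cohort A: 90 × 0.02 = 1.8 to 90 × 0.10 = 9.0.
- Responders, 0.45 × 90 = about 40: 40 × 0.02 = 0.8 to 40 × 0.10 = 4.0.

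Deaths within D2 = 14 weeks (3.22 months) still count. The share dying in that time is 1 − 2^(−3.22/median):

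- median 3 months: 0.525;
- median 6 months: 0.311;
- median 9 months: 0.220.

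Share left: 0.02 × 0.475 = 0.0095 to 0.10 × 0.780 = 0.078. That is 0.9 to 7.0 of 90 participants, and 0.4 to 3.1 of 40 responders, at risk of losing an event by the end of follow-up. The result scales directly with s and with the share of sites that read Table 8-1 literally: if half did, 0.4 to 3.5 of 90. Fewer would be affected at the primary cut-off, which needs about 24 weeks of assessments.

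**The case against.** The strongest reply is that the documents already show what is meant. Section 7.1 lists only one progression reason for required discontinuation, and it is progression by BIRC. Section 8.6.1 describes entry to efficacy follow-up by BIRC progression. Section 8.4.1 drops further scans only once central review confirms progression, and the site is told the result. The paragraph just before the follow-up paragraph of 8.4.1 speaks of initial progression by BIRC. All of this stands, and a careful site would follow Table 1-3.

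A reader might infer that no text on post-treatment imaging names the assessor, and that all three loose texts let scans stop for clinical progression. The documents do not support that. Section 8.6.1 names BIRC, the 8.4.1 paragraph requires RECIST 1.1 and points to Table 1-3, and 7.1.2 requires documented progression.

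It can also be said that such stops may be rare. Sections 10.8.4.2 and 10.8.4.4 belong to a generic sponsor guideline, which asks that progression stops without RECIST documentation be carefully reviewed. A row in SAP Table 2-6 provides for a case without predicting how often it occurs. The exception in 8.4.1 concerns an immediate change of therapy, after which DOR and PFS are censored in any event. These points limit the size. They do not remove the conflict in Table 8-1.

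Investigator-assessed DOR and PFS and the PFS concordance table (SAP 2.7.6, 2.8.1.4) would show some of the discordance, but they cannot recover BIRC events that were never imaged.

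**Conclusion.** The point holds as a minor internal conflict. Table 8-1, read literally, lets a site end imaging after local or clinical progression that BIRC did not confirm, while the rest of the protocol requires scans until BIRC progression. In participants without new therapy, or before it starts, BIRC progressions and deaths later than D2 could be lost from DOR and PFS by informative censoring.

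The size cannot be derived from the documents, because they give no rate of such stops. The illustrative 0.9 to 7.0 of 90 should not be read as an estimate: it rests on assumed stop and survival rates and on every site taking the literal reading. A few participants at most is the more plausible size.

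A reader might also infer that the trial's efficacy conclusion is at risk. It is not. Success and futility rest on ORR, which is not materially affected, and DOR and PFS are Kaplan-Meier estimates with no test or success threshold.

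**What to change.** In every post-treatment entry of Table 8-1 (the body row and both brain entries), qualify disease progression as per RECIST 1.1 and confirmed by BIRC, leaving the other exclusions as they are. For consistency, add by BIRC after RECIST 1.1 in the efficacy follow-up paragraph of 8.4.1, and make the opening clause of 7.1.2 refer to progression documented by BIRC.

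The cost is a few words in three places and follow-up scans in a few participants, all of which Table 1-3 already requires. Some of these participants will be too unwell to attend, so not every event would be recovered.
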